12. PLANS FOR DISSEMINATING AND COMMUNICATING STUDY RESULTS

In the event of any prohibition or restriction imposed (eg, clinical hold) by an applicable competent authority in any area of the world, or if the investigator is aware of any new information which might influence the evaluation of the benefits and risks of a Pfizer product, Pfizer should be informed immediately.

The results of this study are not part of any regulatory submission. The results of this study will be submitted for abstracts and publications. The final output will be filed in Pfizer’s Global Document Management System upon final study completion. This study will be registered in the ClinicalTrials.gov, etc. and the information will be disclosed.

15. LIST OF FIGURES

None

ANNEX 1. LIST OF STAND ALONE DOCUMENTS

Appendix 1. Organization of study operation

ANNEX 2. ENCEPP CHECKLIST FOR STUDY PROTOCOLS

Not applicable.

ANNEX 3. ADDITIONAL INFORMATION

Appendix 2. Inclusion and Exclusion criteria in J-Ph2

Appendix 3. Each patient status at last visit of J-Ph2

Appendix 2. Inclusion and Exclusion criteria in J-Ph2

Inclusion criteria

1. Adult women (≥ 20 years of age) with proven diagnosis of adenocarcinoma of the breast with evidence of locoregionally recurrent or metastatic disease not amenable to resection or radiation therapy with curative intent and for whom chemotherapy is not clinically indicated.
2. Documentation of histologically or cytologically confirmed diagnosis of ER(+) breast cancer based on local laboratory results.
3. All patients must agree to provide tumor tissues for centralized retrospective confirmation of ER status and to evaluate correlation between genes, proteins, and RNAs relevant to the cell cycle pathways and sensitivity/resistance to the investigational agents. Freshly biopsied, recurrent/metastatic tumor samples must be provided whenever possible. If such a biopsy is not feasible or cannot be safely performed, then an archived tumor sample may be accepted. In either case a formalin fixed, paraffin embedded (FFPE) block or 12 unstained FFPE slides are required for patient participation.
4. Previously untreated with any systemic anti-cancer therapy for their locoregionally recurrent or metastatic ER(+) disease.
5. Postmenopausal women defined as women with:
 - Prior bilateral surgical oophorectomy, **or**
 - Medically confirmed post-menopausal status defined as spontaneous cessation of regular menses for at least 12 consecutive months (and follicle-stimulating hormone [FSH] and estradiol blood levels in their respective postmenopausal ranges with no alternative pathological or physiological cause, if applicable).
6. Measurable disease as defined per RECIST v.1.1 or bone-only disease (with bone lesions confirmed by Computed Tomography [CT], Magnetic Resonance Imaging [MRI] or bone X-ray). Tumor lesions previously irradiated or subjected to other locoregional therapy will only be deemed measurable if disease progression at the treated site after completion of therapy is clearly documented.
7. ECOG PS 0-2.
8. Adequate bone marrow and organ function defined as follows:
 - ANC $\geq 1,500/\text{mm}^3$ ($1.5 \times 10^9/\text{L}$);
 - Platelets $\geq 100,000/\text{mm}^3$ ($100 \times 10^9/\text{L}$);

- Hemoglobin ≥ 9 g/dL (90 g/L);
- Serum creatinine $\leq 1.5 \times$ ULN or estimated creatinine clearance ≥ 60 mL/min as calculated using the method standard for the institution;
- Total serum bilirubin $\leq 1.5 \times$ ULN ($\leq 3.0 \times$ ULN if Gilbert's disease);
- AST and/or ALT $\leq 3 \times$ ULN ($\leq 5.0 \times$ ULN if liver metastases present);
- Alkaline phosphatase $\leq 2.5 \times$ ULN ($\leq 5.0 \times$ ULN if bone or liver metastases present).

9. Resolution of all acute toxic effects of prior anti-cancer therapy or surgical procedures to NCI CTCAE version 4.0 Grade ≤ 1 (except alopecia or other toxicities not considered a safety risk for the patient at investigator's discretion).

10. Willingness and ability to comply with scheduled visits, treatment plan, laboratory tests, and other study procedures.

11. Evidence of a personally signed and dated informed consent document indicating that the patient (or a legal representative) has been informed of all pertinent aspects of the study before any study-specific activity is performed.

Exclusion criteria

1. HER2-positive tumor as defined by documentation of erbB-2 gene amplification by FISH (as defined by a HER2/CEP17 ratio ≥ 2) or chromogenic in situ hybridization (CISH, as defined by the manufacturer's kit instruction) or INFORM HER2 dual ISH (as defined by manufacturer's kit instruction) or documentation of HER2-overexpression by IHC (defined as IHC3+, or IHC2+ with FISH or CISH confirmation) based on local laboratory results utilizing one of the sponsor-approved assays. If HER2 status is unavailable or was determined using a test other than a sponsor-approved assay, then testing must be performed/repeated using one of these assays prior to study registration. If tissue sample from both primary and recurrent/metastatic tumors are available, HER2 assessment from the most recent sample (i.e., recurrent/metastatic sample) should be used to define eligibility whenever feasible.
2. Patients with advanced, symptomatic, visceral spread, that are at risk of life-threatening complications in the short term (including patients with massive uncontrolled effusions [pleural, pericardial, peritoneal], pulmonary lymphangitis, and over 50% liver involvement).
3. Known active uncontrolled or symptomatic CNS metastases, carcinomatous meningitis, or leptomeningeal disease as indicated by clinical symptoms, cerebral edema, and/or progressive growth. Patients with a history of CNS metastases or cord compression are eligible if they have been definitively treated with local therapy (eg, radiotherapy,

stereotactic surgery) and are clinically stable off anticonvulsants and steroids for at least 4 weeks before study registration.

4. Prior neoadjuvant or adjuvant treatment with a non-steroidal aromatase inhibitor (ie, anastrozole or letrozole) with disease recurrence while on or within 12 months of completing treatment.
5. Prior treatment with any CDK4/6 inhibitor.
6. Patients treated within the last 7 days prior to study registration with:
 - Food or drugs that are known to be CYP3A4 inhibitors (ie, amprenavir, atazanavir, boceprevir, clarithromycin, conivaptan, delavirdine, diltiazem, erythromycin, fosamprenavir, indinavir, itraconazole, ketoconazole, lopinavir, mibefradil, miconazole, nefazodone, neflifavir, posaconazole, ritonavir, saquinavir, suboxone, telaprevir, telithromycin, verapamil, voriconazole, and grapefruit or grapefruit juice);
 - Drugs that are known to be CYP3A4 inducers (ie, carbamazepine, felbamate, nevirapine, phenobarbital, phenytoin, primidone, rifabutin, rifampin, rifapentine, and St. John's wort).
 - Drugs that are known to prolong the QT interval.
7. Major surgery, chemotherapy, radiotherapy, any investigational agents, or other anti-cancer therapy within 2 weeks before study registration. Patients who received prior radiotherapy to $\geq 25\%$ of bone marrow are not eligible independent of when it was received.
8. Diagnosis of any other malignancy within 3 years prior to study registration, except for adequately treated basal cell or squamous cell skin cancer, or carcinoma in situ of the cervix.
9. QTc >480 msec (based on the mean value of the triplicate ECGs), family or personal history of long or short QT syndrome, Brugada syndrome or known history of QTc prolongation, or Torsade de Pointes (TdP).
10. Uncontrolled electrolyte disorders that can compound the effects of a QTc-prolonging drug (eg, hypocalcemia, hypokalemia, hypomagnesemia).
11. Any of the following within 6 months of study registration: myocardial infarction, severe/unstable angina, ongoing cardiac dysrhythmias of NCI CTCAE version 4.0 Grade ≥ 2 , atrial fibrillation of any grade, coronary/peripheral artery bypass graft, symptomatic congestive heart failure, cerebrovascular accident including transient ischemic attack, or symptomatic pulmonary embolism.

12. Active inflammatory bowel disease or chronic diarrhea, short bowel syndrome, or any upper gastrointestinal surgery including gastric resection.
13. Known hypersensitivity to letrozole, or any of its excipients, or to any PD-0332991 excipients.
14. Known human immunodeficiency virus infection.
15. Other severe acute or chronic medical or psychiatric condition or laboratory abnormality that may increase the risk associated with study participation or investigational product administration or may interfere with the interpretation of study results and, in the judgment of the investigator, would make the patient inappropriate for entry into this study.
16. Patients who are investigational site staff members or relatives of those site staff members or patients who are Pfizer employees directly involved in the conduct of the trial.
17. Participation in other studies involving investigational drug (s) (Phases 1-4) within 2 weeks before study registration and/or during participation in the active treatment phase of the trial.
18. Recent or active suicidal ideation or behavior.

1 INTRODUCTION

This analysis plan describes data summaries and details of statistical analyses for the “multicenter, retrospective, observation study to evaluate palbociclib plus letrozole for overall survival in Japanese subjects with HR-positive/HER2-negative advanced breast cancer.” Planned protocol outlines may be modified in this analysis plan; in which case, any changes made in the analytical methods or the definition of the primary endpoint shall also be reflected to the protocol.

2 STUDY OBJECTIVES

Primary Objective

To evaluate first-line palbociclib plus letrozole for overall survival (OS) in Japanese subjects with HR-positive/HER2-negative advanced breast cancer.

Secondary Objective

To investigate the types and duration of subsequent treatment following palbociclib plus letrozole therapy in Japanese subjects with HR-positive/HER2-negative advanced breast cancer.

3 STUDY DESIGN

This is a Japanese, multicenter, retrospective, observation study. This observation study is designed as a follow-up study to the Japanese phase 2 study of palbociclib (NCT01684215, the phase 2 part of Study A5481010; hereinafter, J-Ph2). In J-Ph2, 43 subjects were enrolled and 42 received palbociclib plus letrozole. Eight deaths were reported at the end of J-Ph2 (i.e., last subject last visit [LSLV], October 25, 2018). Of the remaining 34 subjects with no reported deaths, 4 refused further follow-up and 30 were being followed up for survival.

Medical charts of those 30 subjects in the post-J-Ph2 survival period will be used to retrospectively collect OS and subsequent-treatment data. For subjects transferred to another hospital, the investigator will be requested to make his/her utmost efforts to collect data from the hospitals to which the subjects were transferred. The investigator will complete paper-based case report forms (CRFs) at the start of the study at each site and during the annual reporting period specified by the sponsor. Subject IDs assigned in J-Ph2 will be used to collate the subject demographics and other relevant data between this observation study and J-Ph2 and to analyze the data.

Eight subjects with OS events confirmed in J-Ph2 and 4 who refused to continue follow-up after J-Ph2 will be analyzed based on data collected in J-Ph2.

3.1 Timing of analysis

In this study, data will be collected continuously until a sufficient number of OS events are available to determine the median OS. The number of OS events will be calculated for each annual reporting period; the primary endpoint will be analyzed only once.

4 DEFINITIONS OF ENDPOINTS AND BASELINE VARIABLES

4.1 Primary Endpoint

Overall survival (OS)

Defined as time from the date of the first dose of the investigational product in J-Ph2 to the date of any-cause death. Subjects whose death was unconfirmed will be censored at the last date of confirmed survival.

4.2 Secondary Endpoints

Overview of Subsequent Treatment

Subsequent treatment subject to data collection will be limited to systemic therapies prescribed by physicians for advanced breast cancer (chemotherapies, hormone therapies, molecular targeted drugs, etc.).

- Percentage of subjects by types of subsequent treatment (category: endocrine therapy-based, chemotherapy-based, others)
- Percentage of subjects by treatment line (category: no subsequent treatment, first subsequent treatment, second subsequent treatment)

Subsequent-treatment period

Defined as time from the start date to the end date of each line of treatment among subjects who received subsequent treatment. If "Ongoing" is checked for the latest record of an applicable subsequent treatment, data will be cut off at the date on which the CRF with "Ongoing" is fixed.

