9.4.2. Data collection time point and Data collection period

In this study, data will be collected with paper-based CRFs. The Investigator will complete CRFs for all the patients who remain in follow-up and submit them to the sponsor at the below time points;

1. Study initiation at each study site
2. Annual reporting period set by the sponsor (eg, every April)

For each patient, data collection will be continued until death unless patients withdraw consent or if the study gets sufficient OS events.

For the study, data collection will be continued until sufficient number of OS events are obtained to determine median OS.

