9.6. Data management

Investigators will fill out relevant CRFs based on source documents (eg, patients' medical chart) with a pen, ballpoint pen, etc. After the completion of CRFs, the investigator will promptly submit them to the sponsor by mail.

When receiving a query from the sponsor on the completed CRF (ie, Data Clarification Form [DCF]), investigators will reconfirm the information on source documents, fill out the DCF as required, and submit the DCF to the sponsor.

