9.6.1. Case report forms (CRFs)/Data collection tools (DCTs)/Electronic data record

As used in this protocol, the term CRF should be understood to refer to either a paper form or an electronic data record or both, depending on the data collection method used in this study.

A CRF is required and should be completed for each included patient. The completed original CRFs are the sole property of Pfizer and should not be made available in any form to third parties, except for authorized representatives of Pfizer or appropriate regulatory authorities, without written permission from Pfizer. The investigator shall ensure that the CRFs are securely stored at the study site in paper form and will be secured in a locked room to prevent access by unauthorized third parties.

The investigator has ultimate responsibility for the collection and reporting of all clinical, safety, and laboratory data entered on the CRFs and any other data collection forms (source documents) and ensuring that they are accurate, authentic/original, attributable, complete, consistent, legible, timely (contemporaneous), enduring, and available when required. The CRFs must be signed by the investigator or by an authorized staff member to attest that the data contained on the CRFs are true. Any corrections to entries made in the CRFs or source documents must be dated, initialed, and explained (if necessary) and should not obscure the original entry.

The source documents are the hospital or the physician's chart. In these cases, data collected on the CRFs must match those charts.

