4.3 Other Endpoints

Clinical efficacy of subsequent treatment (categories: complete response, partial response, stable disease, progression, unknown)

- Percentage of subjects applicable to each category of clinical efficacy by each type of subsequent treatment
- Percentage of subjects applicable to each category of clinical efficacy by each treatment line

Time to start of chemotherapy

Defined as time from the date of the first dose of the investigational product in J-Ph2 to the date of the first subsequent chemotherapy or any-cause death, whichever occurred first. Surviving subjects who had not started subsequent chemotherapy will be censored at the last date of confirmed survival.

Dose Adjustment of Palbociclib

- Percentage of subjects by types of dose reduction (category: no dose reduction, dose reduction by 1 level to 100 mg, dose reduction by 2 levels to 75 mg, others)
- Percentage of subjects by reasons for dose reduction (category: adverse event, others) among those who reduced doses

Duration of Treatment with Palbociclib + Letrozole

The duration of treatment with palbociclib per dose (category: 125 mg, 100 mg, 75 mg, etc.) is defined as time from the date of the first dose to the end of treatment with the dose level.

The duration of treatment with letrozole is defined as time from the date of the first dose per investigational product in J-Ph2 to the date of the last dose of letrozole.

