6.3 Handling of missing data

6.3.1 Missing dates

If the start or end day of subsequent treatment, the end day of palbociclib, or the end day of letrozole is missing, the “first day” will be imputed. Missing year or month will not be complemented.

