7.2 Secondary Endpoints

Percentage of subjects receiving subsequent treatment

The number and percentage of subjects will be calculated for treatment lines (First, Second) and types of subsequent treatment. Changes in subsequent treatment in subjects who proceeded to receive subsequent treatment will be summarized and plotted on graphs.

Subsequent-treatment period

Data for each treatment line will be summarized using a Kaplan-Meier method and plotted on graphs. The duration of subsequent-treatment period for each treatment line will be estimated for median and 95%CI. The same analyses will be performed for each type of subsequent treatment per treatment line.

The duration of all subsequent treatment will be plotted for each subject.

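### SAP 4.2 cuts off an ongoing line of subsequent therapy at an undefined form date, which can fall after the patient was last known alive

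*SAP*

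**What the plan says.** SAP 4.2 defines the subsequent-treatment period as the time from the start to the end of each line. For a line whose latest record is marked 'Ongoing', "data will be cut off at the date on which the CRF with 'Ongoing' is fixed". SAP 7.2 then analyses each line by Kaplan-Meier: "The duration of subsequent-treatment period for each treatment line will be estimated for median and 95%CI". It also plots every line for every patient. Protocol 9.7.3 plans the same Kaplan-Meier medians and adds no cut-off rule.

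The two other long-term time-to-event endpoints use a patient-level date. For overall survival (SAP 4.1): "Subjects whose death was unconfirmed will be censored at the last date of confirmed survival". For time to chemotherapy (SAP 4.3): "Surviving subjects who had not started subsequent chemotherapy will be censored at the last date of confirmed survival".

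Forms are completed at study initiation and then at each "Annual reporting period set by the sponsor (eg, every April") (Protocol 9.4.2). On handling, Protocol 9.6 says: "After the completion of CRFs, the investigator will promptly submit them to the sponsor by mail". The sponsor may then raise queries. Protocol 9.6.1 adds: "The CRFs must be signed by the investigator or by an authorized staff member". Table 2 of the protocol collects therapy start and stop dates, the date last known alive and the date of death. It lists no 'fixed' date and no date last known on therapy.

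**The concern.** Completion, signature, mailing, query resolution and data lock could each be called the date a form is fixed, and two programmers could choose differently. Several of these come after the last chart entry that shows the patient on treatment. For patients who have transferred, Protocol 9.9 accepts that data may be incomplete, so the gap could be longer.

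A stop that happens inside the gap is not seen, yet the gap counts as time on treatment. The median duration by line, its confidence interval, the first-line subgroup curves in SAP 7.4 and the per-patient plots would all carry that extra time. One dataset could show a patient on therapy after the last date on which it confirms she was alive.

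**Working it through.** The plan states no duration, lag or ongoing share, so there is no figure to reproduce. The check has three parts: direction, size for a large sample, and size against precision.

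**Direction.** Compare censoring at the last chart evidence with censoring at a later form date. Observed stops do not move; only censoring times move later. At each observed stop the number at risk, n, is therefore the same or larger, so each Kaplan-Meier factor 1 − 1/n is the same or larger. The curve is the same or higher, and the median is the same or later. This concerns this one rule, not the net bias of the endpoint.

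**Which lines are exposed.** Only lines still ongoing on the latest form. A stop missed in one year can be entered with its real date at the next annual report.

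**Size, large sample.** All inputs are assumptions except the calendar anchors:
- Line duration is exponential with true median 12 months, so λ = ln 2/12 = 0.0578 per month.
- Line starts are uniform over the W months before the last chart evidence.
- The form date falls g months after that evidence.
- Anchors from the documents: J-Ph2 last visit, 25 October 2018, to start of data collection, 15 December 2020, is 25.7 months; to interim completion, 15 December 2022, 49.7 months; to planned end of data collection, 31 December 2024, 74.2 months.
- W = 110 is assumed, to allow lines that began before the J-Ph2 last visit.

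Let G = 1 − t/W. For t > g the estimated hazard is

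h(t) = λG/(G + k), with k = (e^{λg} − 1)/(λW),

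and t replaces g in k when t ≤ g. The Kaplan-Meier median is the time at which the integral of h reaches ln 2. The ongoing share is (1 − e^{−λW})/(λW).

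For W = 74 and g = 3: k = (e^{0.1733} − 1)/(0.0578 × 74) = 0.1892/4.274 = 0.0443. At t = 6, G = 0.919, so the hazard is multiplied by 0.919/(0.919 + 0.0443) = 0.954. Integrating gives a median of 12.5 months.

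| Line starts (months back) | Ongoing | Lag 0 | Lag 1 | Lag 3 | Lag 6 |
|---|---|---|---|---|---|
| 26–74 | 8% | 12.0 | 12.0 | 12.0 | 12.0 |
| 0–110 | 16% | 12.0 | 12.1 | 12.3 | 12.6 |
| 0–74 | 23% | 12.0 | 12.2 | 12.5 | 13.0 |
| 0–50 (interim) | 33% | 12.0 | 12.3 | 12.8 | 13.5 |

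The 26–74 row does not move because no line is censored before 26 months, well after the median. Simulation of 1,000,000 lines per scenario agrees with the table to within 0.1 month. With a true median of 6 months and W = 74, the values at lags 1, 3 and 6 are 6.1, 6.2 and 6.3.

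**Size against precision.** I took 30 lines, W = 74, true median 12, a 3-month lag and 5,000 simulated runs. The mean shift is +0.5 months. There is no shift in about two thirds of runs and never a fall. The sampling SD of the median is about 3.4 months.

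**The case against.** The strongest reply is that the form date is the right kind of date. Treatment duration needs on-treatment status, and a signed form marked 'Ongoing' speaks to that directly, whereas a date last known alive does not. If 'fixed' means site completion with therapy confirmed that day, the date effect is close to zero. Protocol 9.6 asks for prompt submission, and answering a query sends the investigator back to the source documents, so a query may refresh the evidence as well as delay the form. Lags of 3 or 6 months have no support in the documents.

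Most of this stands. A different rule from overall survival is not in itself an error, and the effect may be nil. What remains is that the SAP does not say which date it means, and nothing stops that date from passing the last date on which the patient was known alive. No line can be shown to continue beyond that point.

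A reader might also infer three stronger things:

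- **That the event is undefined, so a cut-off line could be counted as a stop.** The SAP does not spell out the coding. But a period running from start to end date, a cut-off only for 'Ongoing' lines and a Kaplan-Meier analysis together point to the recorded end as the event and 'Ongoing' as censored.
- **That deaths on treatment will be censored.** No such rule is written. Tables 3 and 4 require a Subsequent therapy form at death, and a stop date entered there closes the line.
- **That annual reporting builds in a lag of up to a year for every line.** A later report can correct an earlier one, so only the latest record counts.

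**Conclusion.** The point holds as a minor one. The stated rule uses an undefined administrative date and can only leave the Kaplan-Meier duration by line unchanged or raise it. With a true median of 12 months, the effect at the planned end of data collection is 0 to about +0.5 months for a lag of 1 to 3 months. That is small beside a sampling SD of about 3.4 months for 30 lines. It would be larger at the interim, when more lines are open. These sizes rest on assumed exponential durations, uniform starts and lags that the documents do not give.

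The study is descriptive and the endpoint is secondary. Overall survival has its own censoring date and is not affected. The case for change is that a better cap is already collected, not that the bias is large.

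**What to change.** Amend SAP 4.2 with three statements that do not overlap:

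1. **Patient not known to have died.** Censor a line marked 'Ongoing' on its latest record at the earlier of the form date and the date last known alive from the Survival status form of the same reporting period. Say which form date is meant, for example site completion or signature.
2. **Patient who has died with the line still open.** End the line no later than the date of death and give one coding. I suggest an event at death, since treatment has ended by then.
3. **The 8 J-Ph2 deaths and the 4 patients who refused further follow-up.** They have no form in this study. Apply the same caps, using the J-Ph2 date of death or last date known alive.

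The cost is SAP wording. Table 2 already collects both dates. For the patients followed in this study, Tables 3 and 4 require the Survival status and Subsequent therapy forms together once palbociclib plus letrozole has stopped, including at death. Protocol 9.7.3 states no cut-off rule that would conflict. Protocol 9.6.1 requires a signature but does not say that it is dated, so a site date needs confirming; the cap works without it.

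The downside is that reported durations may be slightly shorter. Some upward bias can also remain, because being alive does not confirm being on treatment: about +0.1 to +0.2 months for a remaining 1-month gap in the 0–110 and 0–74 windows.
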